9.6. Follow-Up Visits

Table 3 below specifies permitted time windows for the required subject visits. Subject visit target dates and windows for each follow-up will be made available to the study site. Follow-up visit windows are based on days post-acute MI, and the follow-up visit can be performed either in person or via phone. If a subject visit fall outside the pre-specified window, a study deviation must be reported and the original follow-up schedule maintained for subsequent visits.

Data analyses will include follow-up visits, regardless of whether the visits occur within the time window. Therefore, a late visit is preferred over a missed visit but must be accompanied by a deviation.

Table 3: Follow-up windows

Study Follow-up Visit	Window (Calculated days post-acute MI)		
	Window Start (days post-MI)	Target (days post-MI)	Window End (days post-MI)
3 month	40	90	120
6 month	150	180	210
12 month	335	365	395

Complete a Subject Visit CRF for each follow-up visit.

At 3-month follow-up visit, LVEF will be assessed as per standard practice:

- As per Investigator's discretion, if the subjects have LVEF $\leq 40\%$ or meeting one of the referral criteria (sustained VT, cardiac or unexplained syncope, clinically significant palpitations, new onset bundle branch block, conduction abnormalities, or symptomatic bradycardia), the subjects can be referred for SCD risk stratification and management (EP Referred Group). If the referral does not take place, it is not a study deviation.
- If the subjects have LVEF $>40\%$ but $<50\%$ (between 41% - 49%), the subjects will remain in the Non-Referred Group.
- If the subjects have LVEF $\geq 50\%$, they shall be exited from the study.

For the Non-Referred Group, a Referral Status CRF is needed for each subsequent visit unless the subject is referred to the EP Referred Group. During study follow-up visits, the Non-Referred Group subjects can be referred to the EP Referred Group if their LVEF is $\leq 40\%$ or meets one of the referral criteria (as listed above).

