9.7. Study Exit

At 3-month follow-up, if a subject has an LVEF $\geq 50\%$, the subject will be exited from the study. Subject who remain in the study after 3-month follow-up should remain in the study until the 12-month follow-up is completed or until all data required to meet study objectives have been collected (whichever comes first). Either an in-office visit or phone call is required for study exit.

A study exit eCRF is required for all subjects. Prior to exiting a subject from the study, it is recommended to follow the subject until all AEs are resolved. Following exit, subjects will continue to receive standard medical care. Upon exiting from the study, no further study data will be collected or study visits will occur for the subject. Exited subjects will not be replaced with newly enrolled subjects.

Subjects are urged to remain in the study as long as possible, but may be exited from the study for any of the following situations:

- Study closure
- Subject lost to follow-up (refer to Section 9.11.1)
- Subject did not meet inclusion/exclusion criteria
- Subject did not provide consent or data use protection authorization
- Subject chooses to withdraw (refer to section 9.11.2 for more information)
- Investigator deems withdrawal necessary (e.g. medically justified, inclusion/exclusion criteria not met)
- Subject exited study at the 3 months visit if the 3-month LVEF is $\geq 50\%$
- Subject completed study after 12 months visit
- Subject Death

For study exit visits the following information is required:

- Reason for exit
- Final interrogation file (or CareLink transmission) for subjects implanted with Medtronic device
- Cardiovascular Adverse events, Study Deviations and System Modification

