6.1 Sample Size Assessment

The sample size calculation was based on the width of the 95% confidence interval for the proportion of subjects that is referred for SCD risk stratification and management among subjects who have a reason for referral at the 3 months visit. The following assumptions were made:

- Drop-out and mortality rate combined from enrollment to 3 months visit of 10%,
- At the 3 months visit, 30% of subjects will have a reason for referral.

Under these assumptions, enrollment of approximately 200 patients per region is needed, to have at least 80% power to achieve a 95% confidence interval width of 25% when 70% of patients with a reason for referral at the 3 months visit is referred for SCD risk stratification and management.

The sample size has been computed as follows.

First, the number of subjects needed in each region with a reason for referral at the 3 months visit ($N_{\text{reason_referral}}$) was computed using the SAS procedure below:

```
proc power;
onesamplefreq
  ci = wilson
  halfwidth = 0.125
  probwidth = .
  proportion = 0.70
  ntotal = 40 to 70 by 1;
run;
```

where proportion = 0.70 is the proportion of subjects to be referred among those with a reason for referral and halfwidth = 0.125 is half of the 95% confidence interval around this proportion. As a result of the above SAS procedure, the needed number of subjects that will give at least 80% power to achieve a 95% confidence interval of halfwidth = 0.125 around a proportion of 70% of subjects with a reason for referral that will be referred is $N_{\text{reason_referral}} = 54$.

Secondly, the number of subjects expected at the 3 months visit was computed as the ratio between the required number of subjects with a reason for referral at the three months visit ($N_{\text{reason_referral}} = 54$) and the assumed proportion of subjects with a reason for referral at the three months visit ($\text{prop}_{\text{referral_assumed}} = 0.30$) :

$$N_{\text{3months}} = \frac{N_{\text{reason_referral}}}{\text{prop}_{\text{referral_assumed}}} = \frac{54}{0.30} = 180$$

The number of subjects to be enrolled was then computed as the expected number of subjects that will complete the three months visit ($N_{\text{3months}} = 180$) and the assumed proportion of subjects that will not drop-out or die between enrollment and the 3 months visit ($1 - \text{rate}_{\text{exit_assumed}} = 0.90$):

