7.9.1.3 Analysis Methods

Subjects will be evaluated during their three months visit (chronic phase, $\geq 40-90$ days after MI) for determination of the need for SCD risk stratification and management. As of this visit, subjects will be partitioned into several groups: died of cardiovascular causes prior to reaching the 3 months visit, exited or died of non-cardiovascular or unknown causes prior to reaching 3 months visit, reached the 3 months visit and exited because of $\text{LVEF} \geq 50\%$, reached the 3 months visit and had at least one reason for referral for SCD risk stratification and management, reached the 3 months visit and had no reason for referral for SCD risk stratification and management.

Subjects classified as “died of cardiovascular causes” will be all subjects with subject status “death” within the exit CRF and with primary cause of death “non-sudden cardiac death” or “sudden cardiac death” within the death CRF.

Subjects classified as “exited or died of non-cardiovascular or unknown causes” will be all subjects with subject status “death” within the exit CRF and with primary cause of death “non-cardiovascular death” or “unknown classification” within the death CRF and all subjects with subject status “adverse event, lost to follow-up, physician decision, sponsor request or withdrawal by subject” in the exit CRF.

Subjects classified as “reached the 3 months visit and exited because of $\text{LVEF} > 50\%$ ” will be all subjects that will have completed the three months visit and will have subject status “other” within the exit CRF and will have a result of LVEF measurement higher or equal than 50% within the LVEF CRF.

Subjects classified as “reached the 3 months visit and had at least one reason for referral” will be all subjects that will have completed the three months visit and that in the referral CRF will have answer “yes” to the question “does the subject meet referral criteria” and will have at least one reason for referral selected underneath the question “if yes, indicate referral criteria met”.

Subjects classified as “reached the 3 months visit and had no reason for referral” will be all subjects that will have completed the three months visit and that will have answer “no” to the question “does the subject meet referral criteria” in the referral CRF.

Descriptive statistics will be used to summarize these groups and displayed as shown in the example Table 2 below.

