Table 2: Number (%) of subject in each group between enrollment and the 3 months visit

		Enrolled Population
Region 1	Died of cardiovascular causes	XX/XX (XX.XX%)
	Exited or died of non-cardiovascular or unknown causes	XX/XX (XX.XX%)
	Reached the 3 months visit and exited because of LVEF \geq 50%	XX/XX (XX.XX%)
	Reached the 3 months visit and had reasons for referral	XX/XX (XX.XX%)
	Reached the 3 months visit and had no reasons for referral	XX/XX (XX.XX%)
Region 2	Died of cardiovascular causes	XX/XX (XX.XX%)
	Exited or died of non-cardiovascular or unknown causes	XX/XX (XX.XX%)
	Reached the 3 months visit and exited because of LVEF \geq 50%	XX/XX (XX.XX%)
	Reached the 3 months visit and had reasons for referral	XX/XX (XX.XX%)
	Reached the 3 months visit and had no reasons for referral	XX/XX (XX.XX%)
...
Overall	Died of cardiovascular causes	XX/XX (XX.XX%)
	Exited or died of non-cardiovascular or unknown causes	XX/XX (XX.XX%)
	Reached the 3 months visit and exited because of LVEF \geq 50%	XX/XX (XX.XX%)
	Reached the 3 months visit and had reasons for referral	XX/XX (XX.XX%)
	Reached the 3 months visit and had no reasons for referral	XX/XX (XX.XX%)

The same summary statistics will be computed at the 6 months and at the 12 months visits and displayed in tables similar to Table 1, except for the group “exited because of LVEF \geq 50%” as patients are exited from the study for this reason at the 3 months visit only.

Note that at the three months visit, subjects with a LVEF \geq 50% will be exited from the study regardless of other reasons for referral. The proportion of those subjects that had a reason for referral other than LVEF will be computed by region and overall.

Among the subjects with a reason for referral during their three months visit, the proportions and Wilson score 95% CI of those who were referred for sudden cardiac death risk (SCD) stratification and management will be computed.

The subjects with a reason for referral (denominator) will be all subjects that at the three months visit will have at least one referral criterion met in the referral CRF. The subjects referred (numerator) will be

all subjects that will have completed the three months visit and that will have answer “yes” to the question “has the subject been referred or invited for SCD risk stratification” in the referral CRF.

An example SAS code for the computation of the proportions for each region is provided below:

```
proc freq data = referral;
  by region;

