7.9.3.3 Analysis methods

At each follow-up visit (3 months, 6 months, 12 months), the proportion of subjects who received an ICD/CRT-D will be computed.

The numerator will be the number of subjects who were implanted at a given follow up visit. In the Implant CRF, these subjects will have answer “yes” to the question “Has the subject received an ICD or CRT-D?”.

The denominator will be either the Enrolled Population or a composite of the below:

- (a) ***all patients meeting an indication for implant and not having been implanted at the previous visits.*** That is, within the Implant CRF form, all subject that at any previous visits will have answer “yes” to the question “did the subject meet an indication for an ICD or CRT-D?”, and at all previous visits will have answer “no” to the question “has the subject received an ICD or CRT-D?”
- (b) ***all patients meeting an indication for implant at the given visit.*** That is, within the referral CRF form, all subject that at a given visit will have answer “yes” to the question “did the subject meet an indication for an ICD or CRT-D?”

A SAS code similar to the example SAS code shown in Section 7.9.1.3 will be used. Separately for each follow up visit, the results will be shown in a table similar to Table 6 below, where “Indicated for an ICD/CRT-D” is the denominator above.

Table 6: Proportion (95% CI) of subjects who receive ICD/CRT-D at visit X

	Enrolled Population		Indicated for an ICD/CRT-D Population	
Region	n/N (%)	95% CI	n/N (%)	95% CI
Region 1	XX/XX (XX.XX%)	(XX.XX% - XX.XX%)	XX/XX (XX.XX%)	(XX.XX% - XX.XX%)
Region 2	XX/XX (XX.XX%)	(XX.XX% - XX.XX%)	XX/XX (XX.XX%)	(XX.XX% - XX.XX%)
...
Overall	XX/XX (XX.XX%)	(XX.XX% - XX.XX%)	XX/XX (XX.XX%)	(XX.XX% - XX.XX%)

In addition to the above analyses, logistic regression models similar to the example model in Section 7.9.1.3 might be fitted overall and by region, to estimate the odds ratios of being implanted, depending on different factors, such as age, gender, specialty of physician who implanted, type of device received – ICD or CRT-D, PCI versus non-PCI, STEMI versus non-STEMI. Results will be displayed either by means of either tables or of plots.

Additional analysis:

A competing risk event curve with accompanying 95% confidence bounds and mortality accounted for, will be produced for each region, to assess a subject's time from enrollment to:

- (a) Having met the referral criteria;
- (b) Having been referred;

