- (c) Having had an SCD stratification visit;
- (d) Having been indicated an ICD/CRT-D implant
- (e) Having received an ICD/CRT-D.

An SAS code for the competing risk analysis similar to the below will be used:

```
proc lifetest data=KM plots=cif(test) timelist=0 1 2 3 4 5 6 7 8 9 10 11 12;
  by region;
  time T*Status(0) /eventcode=1;
  strata Event / order=internal;
run;
```

where Event is a categorical variable with categories the event of interest (meeting the referral criteria, having been referred, having had an SCD risk stratification visit, having been indicated for an ICD/SCD-D implanted, having received an ICD/CRT-D), T is the time in months from enrollment to the date of the event of interest and Status is an indicator variable with 3 values: 0 for censored observations, 1 observations related to the event of interest and 2 observations related to subjects who died. Note that the dataset to be used will contain one row for each event per subject (e.g.: if a subject will have all events, from having met the referral criteria to having received the ICD/CRT-D, the dataset will contain 5 rows for that subject).

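### The regional care-pathway curves censor subjects exited at 3 months for recovered LVEF, which can inflate them and create regional differences that are not real; a second coding beside the planned one is a cheap improvement.

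*SAP*

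**What the plan says.** SAP 7.9.3.3 plans, as an additional analysis, competing-risk curves for time from enrollment to five events: (a) meeting referral criteria, (b) being referred, (c) having an SCD stratification visit, (d) being indicated for a device and (e) receiving one. The curves are to have "mortality accounted for, will be produced for each region". Status is coded "0 for censored observations, 1 observations related to the event of interest and 2 observations related to subjects who died".

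The exit rule stands elsewhere. Under Protocol 9.6, if LVEF at 3 months is 50% or more, subjects "they shall be exited from the study". SAP 7.9.1.3 adds that such subjects "will be exited from the study regardless of other reasons for referral". Protocol 9.7 then says: "Upon exiting from the study, no further study data will be collected or study visits will occur for the subject". Protocol 12.5 does not impute missing data and censors event-free subjects at exit.

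The SAP does identify this group. Its 3-month disposition table (Table 2) counts them by region, using the exit form and the condition that they "will have a result of LVEF measurement higher or equal than 50% within the LVEF CRF". The row is dropped from the later tables "as patients are exited from the study for this reason at the 3 months visit only". The competing-risk curves give them no value of their own.

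**The concern.** Censoring assumes that a subject who leaves would have gone on like those who remain. Here the protocol itself removes subjects on the strength of their LVEF, and an LVEF of 40% or less is one of the reasons for referral. The censoring is therefore tied to the outcome.

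Protocol 12.3.2.3 plans such a curve for implant, and Protocol 12.3.1.3 plans one for indication if any arises at 6 or 12 months. Both serve secondary objectives framed as within 12 months of the MI. The curves are drawn by region, and Protocol 12.1 gives the study's purpose as describing treatment patterns in different geographies. If the share of recovered subjects differs between regions, so does the inflation, and a reader could take it for a difference in care.

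**Working it through.** **What the plan computes.** The documents state no figure for these curves. The sample size, which supplies some inputs, reproduces. At a true proportion of 70%, the probability that the Wilson 95% half-width is at most 0.125 is 0.784 for N = 53 and 0.897 for N = 54. Then 54/0.30 = 180 and 180/0.90 = 200 per region.

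**Inputs.**
- From SAP 6.1: 10% early loss, 30% with a reason for referral ("At the 3 months visit, 30% of subjects will have a reason for referral"), and 70% of those referred. So 0.30 × 0.70 = 21% of attenders are referred.
- From the follow-up windows: the 3-month visit falls on days 40 to 120 after MI, with target day 90. Enrollment is within 30 days of MI.
- Assumed, not in the documents: *f*, the share of 3-month attenders who exit for recovery (20, 35, 50%); and *r*, the recovered subjects' later event rate divided by the stayers' (0 to 1). If 30% have a reason for referral, at most 70% of attenders can exit without one, so the plan allows the assumed range of *f* but does not fix it.

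**Events after the exit visit (for example implant).** Let F be the stayers' later incidence. The all-enrolled value is proportional to (1−f)F + f·r·F. The censored curve applies F to everyone, and the competing coding counts only (1−f)F. So approximately:

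- censored/true = 1/((1−f) + f·r)
- competing/true = (1−f)/((1−f) + f·r)

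| r | censored/true at f = 20 / 35 / 50% | competing/true |
|---|---|---|
| 0 | 1.25 / 1.54 / 2.00 | 1.00 / 1.00 / 1.00 |
| 0.25 | 1.18 / 1.36 / 1.60 | 0.94 / 0.88 / 0.80 |
| 0.5 | 1.11 / 1.21 / 1.33 | 0.89 / 0.79 / 0.67 |
| 1 | 1.00 / 1.00 / 1.00 | 0.80 / 0.65 / 0.50 |

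A simulated Aalen-Johansen estimator checked this for implant. Further assumptions: 30% of referred subjects implanted, the 10% early loss split equally between death and drop-out, 5% later death, 5% later drop-out, and visits triangular on days 40/90/120. Censored/true was 1.24/1.53/1.97 at r = 0, 1.11/1.20/1.32 at r = 0.5 and 0.99 at r = 1. Competing/true was 1.00 at r = 0 and 0.89/0.79/0.67 at r = 0.5.

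**Events recorded mainly at the 3-month visit (criteria met, referred).** A recovered subject seen early leaves the risk set while others have not yet been examined. The estimator then gives that subject the chance of an event at a visit already passed without one. A simulation assumed 30% with the event at the visit, 10% later and no other losses. At *equal* later rates (r = 1), censored/true was about 1.10/1.20/1.37 for f = 20/35/50%. With all visits on one day it was 1.00. At r = 0 with staggered visits it was about 1.16/1.32/1.58.

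**Between regions.** Take two regions with the same true implant incidence, one with f = 40% and one with f = 20%. At r = 0 the first reads 0.80/0.60 = 1.33 times the second. At r = 0.5 it reads (0.80 + 0.10)/(0.60 + 0.20) = 0.90/0.80 = 1.13 times.

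**Against sampling error.** In a region of 200 with r = 0 and the implant assumptions above, the censored curve averaged 7.3/8.9/11.5% and the competing one 5.9/5.8/5.9% (SD 1.7 points, so a half-width of 1.96 × 1.7 = 3.3). The excess of 1.4/3.1/5.6 points is 0.4/0.9/1.7 half-widths. Over the same range of *f* it is 0.3 to 1.1 half-widths if 15% of referred subjects are implanted, and 0.5 to 2.2 if 50% are.

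**The case against.** **Severity.** The SAP labels the curves an additional analysis, the study is descriptive, and *f* and *r* are both assumed. All of that stands. The factor of 2.00 needs f = 50% and r = 0 together, and at f = 20% the implant excess is within one region's sampling error. Table 2 shows recovery exits by region, so a careful reader could see the cause, but nothing planned shows its effect on the curves.

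**The coding is not final.** The SAS code is offered as an example, and T is not defined for censored rows. Protocol 12.5, read literally, also censors deaths that the curves treat as competing, so it does not settle the coding alone. This stands in part: a programmer could do otherwise. But the three stated Status values, with censoring at exit, leave no other documented handling.

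**Competing coding is no cure.** Recovery exit does not prevent a later referral or implant, so treating it as competing answers a narrower question. At r = 0.5 it is 11 to 33% too low for implant, while censoring is 11 to 33% too high. A reader might infer that competing coding is the correct analysis and should replace the planned one. The documents do not support that: which curve lies closer depends on *r*, and nothing is recorded after exit from which *r* could be learned.

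**Conclusion.** The point holds as a conditional one. Followed as written, the curves censor recovered subjects because of the variable that drives referral. For events after the exit visit the curve is too high if these subjects have a lower later rate, by about 1.11 to 2.00 times over f = 20 to 50% and r = 0 to 0.5, and it is close to unbiased at equal rates. For events recorded mainly at the visit, equal later rates are not enough, because staggered visits alone inflate the curve. Regional comparisons are the most exposed, since *f* can differ by region. All sizes rest on assumed values of *f*, *r* and the event rates.

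Two stronger readings are tempting. One is that the curves are certainly too high. For events after the visit that needs r below 1, which is plausible but cannot be checked in this study. The other is that the main results are affected. They are not: the primary Wilson proportion is taken at the 3-month visit among subjects with a reason for referral, and the Enrolled Population columns of Tables 5 and 6 keep these subjects in the denominator. Those columns do not carry this censoring bias, though they too cannot see events after exit. This is a cheap improvement to a secondary display.

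**What to change.** In SAP 7.9.3.3:

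1. Give exit at 3 months for LVEF of 50% or more its own Status value (for example 3), used only if no event is dated on or before the exit visit. Keep 0 for loss to follow-up, withdrawal and end of study.
2. For each region and event, show two curves side by side: the planned one with these exits censored, and one with value 3 as competing, labelled *cumulative incidence before recovery exit*.
3. Report *f* by region with the curves.
4. State that, for events after the exit visit, the two curves approximately bracket the all-enrolled value if recovered subjects' later rate lies between zero and the stayers' rate. The word approximately is needed: at r = 1 the simulated censored curve was 0.99 of the true value. State also that, for events recorded at the visit, visit spread further inflates the censored curve. Do not claim that either coding is closer to the truth.

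No new data are needed. The group is already derived for Table 2, and the planned code, which names 0 as censored and 1 as the event, would treat a value of 3 as competing just as it treats 2. The cost is one extra curve per event and region, and the second curve answers a narrower question than incidence within 12 months. The planned curve stays; under Protocol 12.1 the change and its justification go in the study report.
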